**Table 1: Assessments**

Assessment	Base-line	Month 1	Month 4
Participant Demographics (i.e. gender, age, education)	X		
HIV/STI Testing Rates and Partner HIV/STI Testing Rates	X	X	X
Sexual Risk Behaviors—Self-reported measures of sexual intercourse with/without condoms 	X	X	X
Vulnerability to Risky Sexual Behaviors 	X	X	X
Risk Behaviors Associated with HIV/STIs - Youth Risk Behavior Survey 	X	X	X
HIV Knowledge (HIV-KQ)  (45 item true/false questionnaire)	X	X	X
STI Knowledge (STD-KQ)  (27-item true/false questionnaire)	X	X	X
Subjective Norms 	X	X	X
Intentions 	X	X	X
Attitudes—Multi-dimensional Condom Attitudes Scale (MCAS) 	X	X	X
Self-efficacy in sexual risk behaviors—Sexual Risk Behavior Beliefs and Self-efficacy (SRBBS) Scales 	X	X	X
Condom Self-Efficacy (CUSES)  (28-item Likert scale)	X	X	X
Sexual Communication 	X	X	X
*Satisfaction with game play/acceptability and feasibility (12-item Likert scale) 		X	

5. **Genetic Testing** N/A

6. **Subject Population:** Provide a detailed description of the types of human subjects who will be recruited into this study.

Adolescents ages 14-18 will be recruited into this study.

7. **Subject classification:** Check off all classifications of subjects that will be specifically recruited for enrollment in the research project. Will subjects who may require additional safeguards or other considerations be enrolled in the study? If so, identify the population of subjects requiring special safeguards and provide a justification for their involvement.

- |  |  |  |
|--|--|--|
|  Children   |  Healthy                |  Fetal material, placenta, or dead fetus |
|  Non-English Speaking  |  Prisoners                         |  Economically disadvantaged persons      |
|  Decisionally Impaired |  Employees                         |  Pregnant women and/or fetuses           |
|  Yale Students         |  Females of childbearing potential |  |

NOTE: Is this research proposal designed to enroll children who are wards of the state as potential subjects?

Yes  No

8. **Inclusion/Exclusion Criteria:** What are the criteria used to determine subject inclusion or exclusion?

Inclusion/exclusion criteria: For **both phases**, participants must be Black heterosexual adolescent girls aged 14 to 18 and currently enrolled in high school. For **Phase 2**, participants must also: 1) be able to participate in web-based videogame (willing to sit for 60-minutes/session to play the game); 2) not have been tested for HIV in the past year; and, 3) be able to provide assent/parental/guardian consent.

9. How will **eligibility** be determined, and by whom?

Eligibility will be determined by the research team. If a prospective participant meets the inclusion criteria, they will be eligible to participate in the project.

10. **Risks:** Describe the reasonably foreseeable risks, including risks to subject privacy, discomforts, or inconveniences associated with subjects participating in the research.

The potential risks associated with this study have to do with maintenance of the confidentiality of the identities of the participants enrolled in the study and information relating to them. For focus groups, we will address the risk to confidentiality to participants that are participating in the study and that this cannot be guaranteed given that others will also be participating. However, participants will be told that they should not disclose information about other participants and all participants should respect the privacy of each other. Only participants' ID numbers will be recorded on the electronic assessments themselves to protect confidentiality. Sensitive data is encrypted in transit and in storage. The web data-entry interface allows data entry to be performed from anywhere on the Internet and uses 128-bit secure sockets layer (SSL) security to protect the confidentiality of the data. Playing *InvestiDate* may pose a potential psychological risk in that we address sensitive issues around sexual activity and how HIV/STI is transmitted, and the specifics of how certain

risk behaviors (such as alcohol use) can result in HIV/STI. Additionally, participants may also recognize that they have risked acquiring HIV/STI and may have already acquired these diseases without knowing by confirmatory testing. It also involves interactions with the participants' peers. The assessments and instruments may also present a potential risk given that some of the questions are sensitive in nature and address issues around sexual activity and other risky behaviors.

11. **Minimizing Risks:** Describe the manner in which the above-mentioned risks will be minimized.

A number of precautions will be actively integrated into the research procedures to protect the confidentiality and anonymity of all participants. For participating in Yale's videoconferencing tool, Zoom, participants will be asked to find a secure, private setting, free from others outside the study that may overhear the discussion. All research staff and the staff and volunteers participating in the intervention will be required to complete training in research ethics. Data collection forms will be designated by ID numbers only. A separate master file of names, addresses, contact persons, and telephone numbers, along with the study ID numbers will be maintained in a locked file cabinet in the research team's offices. All data entry and analyses will be completed with ID numbers only. The study will be explained to others, such as the guardian/parent and program staff as a study of child development that will focus on promoting healthy behaviors. In instances in which data are requested from other sources or it is beneficial to the participant to provide information to another individual or agency (e.g. medical personnel) this will only be done with the written permission of the guardian/parent on a "Release of Information" form stipulating who the information is provided to, or received from. The research staff will follow standard confidentiality procedures for research programs.

The research assistant will be available at all times to provide assistance to the participants, answer their questions, and serve as a resource if any distress or concern arises. The research assistant will be available to assist the participants, the community sites staff, and the research staff member administering the assessments if there appears to be any distress around the questions being asked. If participants need additional or more intensive attention, the research assistant will contact [name], our clinical psychologist on the team, who will consult with the team in order to potentially provide consultation resources to the participant.

12. **Data and Safety Monitoring Plan:** Include an appropriate Data and Safety Monitoring Plan (DSMP) based on the investigator's risk assessment stated below. (Note: the HIC will make the final determination of the risk to subjects.)

- a. What is the investigator's assessment of the overall risk level for subjects participating in this study? Minimal risk
- b. If children are involved, what is the investigator's assessment of the overall risk level for the children participating in this study? Minimal risk
- c. Include an appropriate Data and Safety Monitoring Plan. Examples of DSMPs are available here <http://your.yale.edu/policies-procedures/forms/420-fr-01-data-and-safety-monitoring-plans-templates> for
  - i. Minimal risk
  - ii. Greater than minimal

The principal investigator is responsible for monitoring the data, assuring protocol compliance, and conducting the safety reviews quarterly. During the review process, the research team will evaluate whether the study should continue unchanged, require modification/amendment, or close to enrollment.

The principal investigator or the Human Investigative Committee (HIC) have the authority to stop or suspend the study or require modifications.

This protocol presents minimal risks to the subjects and Unanticipated Problems Involving Risks to Subjects or Others (UPIRSOs), including adverse events, are not anticipated. In the unlikely event that such events occur, Reportable Adverse Events (which are events that are serious or life-threatening and unanticipated (or anticipated but occurring with a greater frequency than expected) and possibly, probably, or definitely related) or Unanticipated Problems Involving Risks to Subjects or Others that may require a temporary or permanent interruption of study activities will be reported immediately (if possible), followed by a written report within 5 calendar days of the Principal Investigator becoming aware of the event to the IRB via the RNI submission process in IRES IRB and any appropriate funding and regulatory agencies. The investigator will apprise fellow investigators and study personnel of all adverse events that occur during the conduct of this research project through regular study meetings and via email as they are reviewed by the principal investigator. We will use procedures to detect and respond to adverse events that ensure prompt discovery of any adverse events and to minimize their effects. There is adequate surveillance and protections to discover adverse events promptly and keep their effects minimal. Data and safety monitoring procedures in this study include collection and monitoring of paper-based questionnaires and an organizational structure of clearly defined tasks assigned to all research personnel involved in the conduct of this study. We will keep a thorough record of research activities and completion of scheduled assessments.

We have established a Data Safety and Monitoring Board (DSMB) composed of two experts, [name] and [name], in clinical trials in young teens and in statistical analysis of clinical trials to oversee the safety and data integrity of this study. DSMB will also review the progress of the study.

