**Setting:** For **Phase 1 and Phase 2**, recruitment and enrollment will take place either in person with partner schools and organizations or remotely either in partnership with schools that have agreed to collaborate with us, or through study advertisements placed on social media. Given our ability to play the videogame and collect data remotely, we are seeking additional partnerships with schools nationwide and recruiting participants individually through social media, including Facebook and Instagram. For Phase 1 (focus groups), recruitment may also take place online through social media platforms, including Facebook and Instagram. Focus groups will take place online through Zoom where participants will be able to see and interact with each other.

Of note, the Principal Investigator, [name] will not be involved in any aspects of consenting participants or their parents, the randomization process, data collection or direct performance of data analysis procedures.

**Participants:** For **both phases**, participants must be Black heterosexual adolescent girls aged 14 to 18 and currently enrolled in high school. For **Phase 2**, participants must also: 1) be able to participate in web-based videogame (willing to sit for 60-minutes/session to play the game); 2) not have been tested for HIV in the past year; and, 3) be able to provide assent/parental/guardian consent.

**Phase 1: Conduct focus groups and playtesting with Black adolescent girls and develop *InvestiDate*** (30 participants): Focus group discussions with Black adolescent girls will inform the new version of the game by providing ideas for content and gameplay around HIV/STI testing, condom use, and sexual risk taking. We have used and refined this iterative process for current videogame projects. Data collected will be used to inform the development of the multiplayer videogame, *InvestiDate*. Example question for the focus groups include, “What are some red flags that teens your age look for when considering dating someone?”, “What are some green flags that teens your age look for when considering dating someone?”, “What might make it difficult for teens your age to get tested for HIV/STIs?”

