Data Analyses General Considerations: Statistical procedures and models for analyzing data have been selected according to the research hypotheses being investigated and the types of data available. In general, we will use two-tailed tests and p-values smaller than 0.05 will be considered to indicate statistical significance. When necessary, however, we will use appropriate adjustment of the level of significance (alpha) to account for multiple statistical tests. All statistical analyses will be conducted on an intention-to-treat sample using either SPSS/SAS statistical packages. Baseline characteristics will be analyzed using descriptive statistics. We will use baseline, one-month, and four-month data to estimate effect sizes for the primary outcome. Given the limited sample size (n=80), we anticipate that the power of this study to identify small but significant effect sizes will be low. A strength of this design is that it provides a number of perspectives from which to view treatment effects, including a treatment condition, a control condition, and a follow-up period. The results will inform the sample size calculation for a subsequent full-scale randomized trial.

We will evaluate the preliminary efficacy of *InvestiDate* at increasing HIV/STI testing and partner HIV/STI testing. We will test the hypothesis that individuals who play *InvestiDate* will report more

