HIV/STI testing and partner testing in comparison to the control condition. We will conduct a longitudinal analysis using a hierarchical linear mixed models approach to compare participants in the intervention group to participants in the control group on reported participant and partner HIV/STI testing from baseline across all follow-up assessments (i.e., baseline, one month and four months). Hierarchical modeling will allow us to account for the fact that the data are nested as the participants will play the game in groups. An advantage of mixed models is that participants with missing data need not be excluded as all available data are used in estimating parameters. We will also use logistic regression models to determine if any relevant baseline variables are associated with improvement in reported HIV/STI testing or partner testing (constructed as a binary outcome (Yes/No)). We plan to evaluate the prognostic significance of a small set of predictor variables (e.g., intentions, attitudes, self-efficacy, social norms, and knowledge) and use them as covariates in the primary analysis. All of these analyses will be exploratory given the study sample size.

SECTION II: RESEARCH INVOLVING DRUGS, BIOLOGICS, RADIOTRACERS, PLACEBOS AND DEVICES
--

- |                    |   |
|--------------------|---|
| A. RADIOTRACERS    |  N/A |
| B. DRUGS/BIOLOGICS |  N/A |
| C. DEVICES         |  N/A |

SECTION III: RECRUITMENT/CONSENT AND ASSENT PROCEDURES
---

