**SECTION IV: PROTECTION OF RESEARCH SUBJECTS**

**Confidentiality & Security of Data:**

1. What protected health information (medical information along with the HIPAA identifiers) about subjects will be collected and used for the research? *Name, Address, Telephone Number, Email Address, reported HIV/STI testing status and test results, sexual activity status*
2. How will the research data be collected, recorded and stored? All data collected from the assessments will be entered directly into the secure web-based system, Yale Qualtrics, which is Yale's enterprise-wide data management system. Research staff will enter the data into the Yale Qualtrics system. To assess acceptability and feasibility, directly following completion of the intervention, we will collect quantitative and qualitative data on the intervention participants' experiences of the game intervention.
3. How will the digital data be stored?  CD  DVD  Flash Drive  Portable Hard Drive  Secured Server  
 Laptop Computer  Desktop Computer  Other
4. What methods and procedures will be used to safeguard the confidentiality and security of the identifiable study data and the storage media indicated above during and after the subject's participation in the study?

Data will be stored in Yale's secured online data collection system, Yale Qualtrics. Paper assessments will be kept in a locked filing cabinet in the PI's office.

All portable devices must contain encryption software, per University Policy 5100. If there is a technical reason a device cannot be encrypted please submit an exception request to the Information Security, Policy and Compliance Office by clicking on url <http://its.yale.edu/egrc> or email [[contact]](mailto:[contact])

5. What will be done with the data when the research is completed? Are there plans to destroy the identifiable data? If yes, describe how, by whom and when identifiers will be destroyed. If no, describe how the data and/or identifiers will be secured.

Data collected in the study will reside in our computerized database and electronic storage mechanisms. All data analyses will be performed under approved HIC protocols. Digital files of the focus groups will be destroyed at the end of the study.

6. If appropriate, has a Certificate of Confidentiality been obtained? A CoC automatically covers this study due to its NIH funding.

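### Does the partner-testing comparison need a change because girls with no partner are eligible and no rule says how they count?

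*Combined protocol and SAP*

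**What the plan says.** Section I.8 (repeated under Participants in Section I.4) sets out who may enter: "participants must be Black heterosexual adolescent girls aged 14 to 18 and currently enrolled in high school". Phase 2 adds willingness to play, no HIV test in the past year, and assent or consent. None of these concerns a partner or sexual activity, and Section I.9 treats the list as sufficient.

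Table 1 measures the girl's own testing and partner testing at baseline, month 1 and month 4. Section I.4 (Phase 2) puts recent partner testing into the randomisation algorithm. The statistical text (Data Analyses General Considerations and what follows) states "All statistical analyses will be conducted on an intention-to-treat sample". It compares the arms by a hierarchical linear mixed model "on reported participant and partner HIV/STI testing from baseline across all follow-up assessments", and for its logistic models it treats testing as a Yes/No outcome. On missing data it says that "participants with missing data need not be excluded as all available data are used in estimating parameters". On use of the findings: "The results will inform the sample size calculation for a subsequent full-scale randomized trial".

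Sexual activity is recorded. Table 1 lists "Self-reported measures of sexual intercourse with/without condoms" at all three visits, and Section IV.1 lists "reported HIV/STI testing status and test results, sexual activity status" among the data held.

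**The concern.** A girl without a partner cannot report a tested partner. The plan leaves two ways to handle her, and they answer different questions.

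- **Scored No.** All randomised girls stay in, but the absolute difference equals the effect among partnered girls multiplied by the partnered share.
- **Treated as missing.** The all-available-data wording could let her drop out. The comparison is then among girls who have a partner after randomisation. A game about judging potential partners could change who that is, so the protection of randomisation is lost.

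At stake is the planning figure for the full trial. Recruitment in this pilot already extends beyond New Haven partner sites: "we are seeking additional partnerships with schools nationwide and recruiting participants individually through social media". If the next trial draws a different mix of girls, an absolute difference carried over without the share would missize it.

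**Working it through.** **Inputs.** From the plan: 40 per arm, two-sided 5%. The plan gives no rates, effect size or power for the 80 girls, so it has no figure to reproduce. Assumed here: partner testing of 10% (control) vs 35% (intervention) among partnered girls; partnered share s of 25%, 40% or 60%; 80% power for the later trial; clustering by play group ignored.

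**1. Unpartnered girls scored No.** Each arm's rate is s times the rate among partnered girls, so the difference is 0.25s and the risk ratio is 0.35s/0.10s = 3.5 at every share. The two-proportion formula with pooled variance gives:

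| Share s | Rates | Difference (points) | n per arm, 80% power | Pilot power, all 40 per arm | Pilot power, partnered only (40s per arm) |
|---|---|---|---|---|---|
| 25% | 2.5% vs 8.75% | 6.25 | 213 | 23% | 26% |
| 40% | 4% vs 14% | 10 | 128 | 34% | 39% |
| 60% | 6% vs 21% | 15 | 81 | 50% | 55% |

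Within the pilot, keeping everyone costs about 3 to 5 points of power on this approximation. The comparison stays randomised.

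**2. Carry-over.** A trial of 81 per arm (planned at s = 60%) has 61% power at s = 40% and 41% at s = 25%. In the other direction, 213 per arm (planned at 25%) has over 99% power at 60%. Other assumed rates agree: for 10% vs 30%, 20% vs 40% and 15% vs 30%, a fall in share from 70% to 40% leaves 52% to 53% power.

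**3. Set against the pilot's precision.** At s = 60% the standard error of the difference is sqrt(0.06×0.94/40 + 0.21×0.79/40) = 0.0745. The 95% interval is 15 ± 1.96×7.45 = 0.4 to 29.6 points. A move from a 60% to a 40% share shifts the difference by 5 points.

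**4. Unpartnered girls treated as missing.** Let t be the proportion of partners tested in both arms, and let a fraction e of untested partnerships end in the intervention arm only. Apparent testing there exceeds t by t/(t + (1−t)(1−e)) − t. For t = 10% this is 1.0 point (e = 10%) or 2.9 points (e = 25%); for t = 30% it is 2.3 or 6.4 points. No extra partner has been tested.

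**5. Which reading does the plan support?** The intention-to-treat sample keeps every randomised girl. The Yes/No construction offers no third category. Every girl also needs a level of the partner-testing factor before she can be randomised. Together these point to No. The all-available-data sentence concerns missing data in general and does not class a girl without a partner as missing.

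**6. Would added analyses help?** Two candidates were checked.

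- *Baseline sexual activity as a covariate.* In simulation, power went from 22.5, 37.7 and 54.0% to 23.5, 38.6 and 56.2% (s = 25, 40, 60%) if activity is stable. If 80% of active girls stay active and 10% of inactive girls start, it went from 25.2, 36.2 and 47.9% to 23.0, 34.1 and 46.7%. That is about −2 to +2 points.
- *Rescaling by the baseline share.* Under the same switching, a baseline share of 60% becomes 0.8×0.60 + 0.1×0.40 = 52% at follow-up, and 25% becomes 0.8×0.25 + 0.1×0.75 = 27.5%. The true differences are 13.0 and 6.9 points. Rescaling by baseline shares gives 13.0×0.25/0.60 = 5.4, or 247 per arm where 192 suffice.

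**The case for a change.** The strongest argument for a change is that exploratory status excuses low power, not an outcome whose denominator is undefined. An analyst could choose between No and missing after seeing the data, and step 4 shows that the second choice can produce an apparent effect of up to 6.4 points. Sizing the next trial is a stated purpose of the pilot, and one sentence plus a table row would cost almost nothing.

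Part of this stands. The rule is not written in the text available, the missing coding would be a poor choice, and an absolute difference quoted without the share could mislead a planner. The randomisation factor, as described, has no separate level for girls with no partner, so it does not balance the partnered share.

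The rest does not carry. A coding sentence would record what an intention-to-treat Yes/No analysis already implies. The plan speaks only of effect sizes and is not tied to an absolute difference; the risk ratio is free of the share, although required enrolment is not. Sexual activity, an imperfect proxy for having a partner, is recorded at every visit, so the active share by arm can be tabulated whenever the next trial is planned. Wider recruitment applies to this pilot and does not show that the next trial's share will differ.

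**Conclusion.** No change follows. This is a gap in detail that analysts fill sensibly: on the most direct reading a girl with no partner counts as No, and the between-arm comparison is then valid. The girl's own testing outcome is unaffected. What remains is a caution for whoever sizes the full trial. The absolute difference scales with the partnered share (6.25 to 15 points across shares of 25% to 60%), and ignoring a fall from 60% to 40% or 25% would leave 61% or 41% power instead of 80%. The data for that check are already collected, and the share over follow-up serves better than the baseline share alone. The added covariate brings no meaningful gain.

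All sizes rest on assumed testing rates, shares and switching, on no clustering, and on an effect among partnered girls that is the same in the new population. The conclusion would weaken if the analysts in fact treated unpartnered girls as missing, which the plan does not direct.
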